6.3 Study Endpoints

6.3.1 Safety Endpoints

The safety and tolerability of casimersen and golodirsen will be assessed through a review and evaluation of the following:

- Adverse events (AEs), serious adverse events (SAEs), deaths, and discontinuations due to AEs
- Laboratory testing may include the following (See Section 9 for complete details):
 - Hematology
 - Coagulation
 - Chemistry
 - Urinalysis
- Cardiac function including ECG and ECHO
- Vital signs
- Physical examination findings

6.3.2 Efficacy Endpoints

6.3.2.1 Primary Efficacy Endpoint

The primary efficacy endpoint is:

- Change from Baseline to Week 48 in dystrophin expression quantified by western blot in muscle biopsy tissue.

6.3.2.2 *Secondary Efficacy Endpoints*

Secondary efficacy endpoints are:

- Change from Baseline to Week 48 in expression of dystrophin as measured by immunofluorescent signal intensity and percent dystrophin positive fibers (PDPF) in muscle tissue sections in comparison to baseline values.
- The efficiency of splicing alteration will be measured by RNA Sequencing (RNA-Seq) to establish DMD mRNA copy number and the exon-exon junction frequency quantified, with normalization to exon junction read values from an exon junction in regions distinct from the targeted exon.

6.3.2.3 *Exploratory Efficacy Endpoints*

Exploratory efficacy endpoints are based on the change from Baseline to Week 48 in the following measures:

- Subjects 6 to 36 months of age at enrollment: Change from baseline in scores on the Bayley Scales of Infant Development – gross motor functions and fine motor functions.
- Change from Baseline to Week 48 in NSAA (subjects 3 years or greater).
- Change from Baseline to Week 48 on the 100M in ambulant subjects over the age of 3.5 years.
- Change from Baseline to Week 48 in ACTIVE-seated for boys over 5 years of age.
- Changes in FVC and FVC% predicted in patients aged ≥ 10 years.
- Peak expiratory flow as reported as % predicted by age and height (%PEF).
- Timed functional tests for ambulant subjects 3 years or older:
 - time to complete 10-meter run
 - time to rise from the floor
 - time to climb 4 steps
 - time to descend 4 steps
- Pediatric Outcomes Data Collection Instrument (PODCI) for patients ages 2-17.
- Adult Patient-Reported Outcomes Measurement Information System (PROMIS) Upper Extremity Report for patients 18+ years.
- Immune staining may be performed on biopsy specimens for members of the dystrophin-associated protein complex, such as the sarcoglycans, dystroglycans and n-Nos.
- Muscle morphometrics may also be performed, including fiber size histograms and quantification of central nucleation.

7 SELECTION AND WITHDRAWAL OF SUBJECTS

7.1 Number of Subjects

Six subjects will be included in this study to be enrolled by invitation. They will receive either casimersen, eteplirsen, or golodirsen according to their genotype.

7.2 Subject Inclusion Criteria

A subject must meet all of the following criteria to be eligible for this study.

1. Is a male with *DMD* and has an out-of-frame duplication of either exon 45, 51, or 53, with a normal copy number of all other *DMD* exons.
2. Is above age 6 months.
3. Has pulmonary function, that in the Investigator's opinion, is unlikely to decompensate significantly over the duration of the study.
4. Has sufficient muscle mass in a pair of bilateral muscles that will allow for pre- and post-treatment muscle biopsies per PI discretion.
5. If the subject is ambulant and 4 years old or greater and has been on a stable dose or dose equivalent of oral corticosteroids for at least 12 weeks prior to Week 1 the dose is expected to remain constant (except for modifications to accommodate changes in weight) throughout the study.

Note: Subjects are allowed to take other medications (excluding other RNA antisense or gene therapy agents) including angiotensin-converting enzyme (ACE) inhibitors, angiotensin receptor blocking agents (ARBs), β adrenergic blockers, potassium, and coenzyme Q, provided they have been on a stable dose for 12 weeks prior to Week 1. The dose is expected to remain constant throughout the study (modifications to doses to accommodate changes in weight are allowed).

6. Has (a) parent(s) or legal guardian(s) who is (are) able to understand and comply with all the study requirements.
7. Is willing to provide informed assent (if applicable) and has (a) parent(s) or legal guardian(s) who is (are) willing to provide written informed consent for the subject to participate in the study.

7.3 Subject Exclusion Criteria

A subject who meets any of the following criteria will be excluded from this study.

1. Any additional missing exon for *DMD* that cannot be treated with study drugs.
2. Subject has previously been treated with eteplirsen, casimersen, or golodirsen, or is currently being treated with other RNA antisense or gene therapy agents.
3. Current or history of liver disease or impairment including:
 - a. an INR value above 1.5
 - b. a total bilirubin greater than 2 times the Upper Limit of Normal (ULN) or a GGT greater than 2 times the ULN
4. Baseline platelet count below the Lower Limit of Normal (LLN) for age.
5. aPPT above the ULN.
6. History of significant medical disorder which may confound the interpretation of either efficacy or safety data e.g., inflammatory disease.
7. Use of any pharmacologic treatment (other than corticosteroids) within 12 weeks prior to Week 1 that may have an effect on muscle strength or function (e.g., growth hormone, anabolic steroids).
8. Current or previous treatment with any other experimental treatment within 12 weeks prior to Week 1.
9. Major surgery within 3 months prior to Week 1 or planned surgery for any time during this study, except for protocol-specified surgery, as applicable.
10. Presence of other clinically significant illness including significant cardiac, pulmonary, hepatic, renal, hematologic, immunologic, or behavioral disease, or malignancy.
11. Use of any aminoglycoside antibiotic or statin within 12 weeks prior to Week 1 or anticipated need for an aminoglycoside antibiotic or statin during the study.
12. QTcF \geq 450 msec based on the Screening and/or Baseline ECG.
13. Prior or ongoing medical condition that could, in the Investigator's opinion, adversely affect the safety of the subject, make it unlikely that the course of treatment would be completed, or impair the assessment of study results. Additionally, subjects who seem unable/unwilling to comply with the study procedures, in the Investigator's opinion, are to be excluded.

14. Acute illness within 4 weeks of the first anticipated administration of study medication which may interfere with study assessments.
15. Symptomatic cardiomyopathy. If the subject is asymptomatic but has a left ventricular ejection fraction <40% at Screening, the investigator should discuss inclusion of subject in the study with the medical monitor.
16. Use of anticoagulants, antithrombotics or antiplatelet agents, previous treatment with investigational drugs within 4 weeks prior to anticipated study drug administration.

NOTE: Potential subjects with abnormal laboratory values may be re-screened for specific laboratory tests within the screening period (the 45 days prior to dosing) before being designated a screen failure. Repeat values within the normal range will be acceptable for inclusion. Additionally, if a subject should have an acute illness within 4 weeks of the first anticipated dose, the PI will discuss with the DSMB about the potential to delay treatment until the illness has resolved.

7.4 Completion of a Subject's Participation in the Study

The length of a subject's participation will be from the time the informed consent form is signed until completion of the End of Study (Week 48) visit (up to 60 weeks).

7.5 Subject Withdrawal Criteria

Any subject can withdraw from study participation at any time for any reason. In addition, the Study Sponsor/Investigator may stop the study participation of any subject at any time. Reasons for study withdrawal include but are not limited to:

- The subject was erroneously included in the study (i.e. was found to have not met the eligibility criteria).
- The subject is unable to comply with the requirements of the protocol.
- The subject participates in another investigational study without the prior written authorization of the Study Sponsor.
- The subject experiences an intolerable or unacceptable AE.

The Investigator or study staff will document the reason(s) for treatment discontinuation on the case report form (CRF).

Subjects who have received at least (1) one dose of study treatment and who are withdrawn from treatment within 28 days after a functional assessment visit will not be asked to return for an End of Study visit (to complete the Week 48 assessments. Subjects who receive at least one (1) dose of study treatment who are withdrawn from treatment more than 28 days after a functional assessment visit will be asked to complete all early termination (Week 48) assessments within approximately 28 days of withdrawal.

Subjects withdrawn from treatment will not be replaced.

7.6 Study Discontinuation

If the Study Sponsor/Investigator, the DSMB, the study monitor, institutional review board/independent ethics committee(s) (IRB), and/or appropriate regulatory officials discover conditions arising during the study that indicate the study should be halted or that the study center should be terminated, appropriate action may be taken after consultation among (at a minimum) the Study Sponsor/Investigator, IRB and the DSMB.

Conditions that may warrant termination of the study or an individual site include, but are not limited to, the following:

- The discovery of an unexpected, serious, or unacceptable risk to subjects enrolled in the study
- A decision by the Drug Manufacturer to suspend or discontinue testing, evaluation, or development of the IP
- Failure of the Investigator to enroll subjects into the study at an acceptable rate
- Failure of the Investigator to comply with pertinent regulations of IRB or appropriate regulatory authorities

- Failure of the Investigator to comply with the protocol
- Submission of knowingly false information from the research facility to the DSMB, the study monitor, IRB or regulatory authorities
- Insufficient adherence to protocol requirements consistent with 21 CFR 312 or the European Clinical Trial Directive 2001/20/EC

Study termination and follow-up will be performed in compliance with the conditions set forth in International Conference on Harmonisation (ICH) E6 on Good Clinical Practice (GCP) as well as 21 CFR 312.56b and the European Clinical Trial Directive 2001/20/EC which require an Investigator's compliance with these requirements and to promptly secure a plan for compliance or discontinue shipment of the IP to the Investigator and end the Investigator's participation in the study.

8 TREATMENT OF SUBJECTS

8.1 Investigational Products

The Investigational Products (IPs) (casimersen, eteplirsen, and golodirsen injection) are supplied as concentrated sterile solutions, which are diluted with 0.9% sodium chloride injection prior to administration via an IV infusion.

Casimersen, eteplirsen, and golodirsen injections are sterile, clear, colorless, isotonic, phosphate-buffered saline (PBS) solutions supplied in single-use 2-mL glass vials containing 2 mL of casimersen, eteplirsen, or golodirsen at a concentration of 50 mg/mL.

8.1.1 Packaging and Labeling

Please refer to the Clinical Study Manual of Operations for information on packaging and labeling. The label text for the study treatments will comply with applicable regional, national, and local laws and regulations and will include at a minimum the contents of the vial, the appropriate regional cautionary statements, lot number, storage conditions, and the name of the Drug Provider (Sarepta Therapeutics, Inc.).

8.1.2 Storage

Store the study treatment at 2°C to 8°C (36°F to 46°F). Do not freeze. Protect from light and store in the original carton until ready for use.

Vials of study treatment must be stored in a secured, limited-access area with appropriate temperature recording, controls, and monitoring. Details for study treatment handling, storage and for preparation of the diluted study treatment for administration can be found in the study-specific Clinical Study Manual of Operations.

8.2 Treatments Administered

Eligible subjects will receive a weekly IV infusion of study treatment (30 mg/kg of casimersen, eteplirsen, or golodirsen, according to genotype) for up to 48 weeks. Subjects will be transitioned to the Sarepta Clinical Transition Program/SareptAssist after the study period for continuous weekly drug access while study sample analysis is pending.

The dose of casimersen, eteplirsen, or golodirsen will be calculated based on the most recent subject weight obtained at the site prior to the current visit. Infusion solutions of casimersen, eteplirsen, or

golodirsen are to be prepared by following the steps detailed in the study-specific Clinical Study Manual of Operations.

- Study treatment will be administered as an IV infusion over a period of approximately 35 to 60 minutes. Patients are to be closely monitored for at least 1 hour following the completion of all infusions. It is recommended that a topical anesthetic cream (e.g. lidocaine 2.5%, prilocaine 2.5%, LMX4 cream, or other per the Investigator's discretion) be applied to the infusion site prior to each administration of study treatment. Additional administration and IP details are available in the study-specific Clinical Study Manual of Operations.

An implanted venous access port may be inserted for study treatment administration at the discretion of the Investigator. After study treatment administration and the saline flush, the port may be flushed with heparin to heparin the port prior to removal of the infusion line. If study treatment is administered into an existing IV line, the line must be flushed with normal saline before and after administration of study treatment.

Subjects will have vital signs measured on infusion days within approximately 30 minutes prior to infusion and approximately 5, 30, and 60 minutes after the end of the infusion. At each infusion, concomitant medications and adverse events will be reviewed.

No other medications may be administered concomitantly during the study treatment infusion. All subjects will be observed for at least 1 hour following the end of each infusion.

The following guidelines for the timing of dosing are to be followed throughout the study:

1. Subjects should receive study treatment once every 7 days starting at the Week 1 Visit.
2. After the first infusion, a window of ± 2 days around the scheduled weekly dosing date (referenced back to the first dose at Week 1) is acceptable.
3. Subjects may not receive 2 separate doses of study treatment within the same 60-hour period.
4. The Principal Investigator is to be contacted in the event of a missed dose.

8.2.1 Dose Modification, Reduction, or Delay

There is no provision for dose alteration in this study. If a subject experiences an AE that requires interruption of administration for ≥ 2 consecutive doses, the Investigator will consult with the DSMB to determine whether the subject may resume treatment.

8.3 **Prior and Concomitant Medications**

Oral corticosteroids, including but not limited to prednisolone and prednisone, for treatment of DMD are required for boys older than 5 years during the course of this study. Subjects entering the study on corticosteroids must have been on a stable dose (or dose equivalent) of oral corticosteroids for at least 12 weeks prior to the first administration of study treatment at Week 1. If clinically necessary, subjects may be allowed to change the corticosteroid compound as long as equivalent dosing is maintained. Doses of corticosteroids are expected to remain constant (except for modifications to accommodate changes in weight) through the completion of study to the degree that is clinically feasible.

Provided they have been on a stable dose for at least 12 weeks prior to Week 1 and the dose is expected to remain constant throughout the study, subjects are allowed to take other medications including:

- Oral ACE inhibitors, including but not limited to perindopril and lisinopril
- Oral β adrenergic blockers, including but not limited to carvedilol and atenolol
- Angiotensin-receptor blockers, including but not limited to losartan, irbesartan, valsartan, and candesartan
- Oral laxatives, including but not limited to lactulose, Senokot, and Movicol
- Vitamin D and calcium supplements
- Alendronate (Fosamax) or other bisphosphonates used to treat osteoporosis/osteopenia by inhibiting osteoclasts
- Over-the-counter preparations such as herbal supplements, vitamins, minerals, and homeopathic preparations

Other concomitant medications (excluding other RNA antisense or gene therapy agents) may also be taken if, in the opinion of the Investigator, they do not interfere with study assessments and outcomes. The Investigator is to contact the DSMB if he/she is unsure of the impact of a concomitant medication on study assessments and outcomes. Every attempt should be made to keep the dosage constant throughout the treatment period (i.e. through Week 48), although modifications to accommodate changes in weight are permitted.

It is recommended that introduction of new physiotherapy interventions during the course of the study be avoided unless the best interests of the subject are at stake. Should a contracture develop during the course of the study, and it is considered in the best interest of the subject to treat the contracture, then any of the following interventions may be used to reduce the contracture, but they must be clearly documented:

- Stretching exercises (passive, active, self)
- Night splints
- Contracture control device
- Serial casting

The following therapies are **not permitted** during the conduct of this study:

- Systemic or oral steroids for non-DMD conditions that, in the Investigator's opinion, could interfere with study assessments and outcomes
- Other investigational agents for the treatment of DMD
- Any medication with the potential to affect muscle mass, strength, and/or function, such as, but not limited to, growth hormone and PDE-5 inhibitors
- Immunosuppressants (other than oral or systemic corticosteroids, as outlined)
- Systemic aminoglycoside antibiotics (unless discussed and agreed upon with the Investigator and the DSMB)
- Statins (unless discussed and agreed upon with the Investigator and DSMB)

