4 INTRODUCTION

4.1 Background of Duchenne Muscular Dystrophy

Duchenne muscular dystrophy (DMD) is a degenerative neuromuscular disease with an X linked recessive inheritance caused by mutations in the dystrophin gene, with a worldwide incidence of approximately 1 in 3500 newborn boys, irrespective of geographical region, race, or population density¹⁻³. The mutations that cause DMD typically disrupt the mRNA reading frame and prevent production of dystrophin, a critically important part of the protein complex that connects the cytoskeleton of a muscle fiber to the cell membrane and extracellular matrix. In the absence of dystrophin, the stress of repeated muscle contraction causes progressive muscle damage. The clinical effect of this disrupted dystrophin reading frame is progressive and ultimately fatal.

DMD is usually first diagnosed between the ages of 3 to 5 years⁴, when toddlers develop a waddling gait, lordosis, toe walking, calf hypertrophy, and a difficulty in climbing stairs. Over time, ambulation becomes increasingly abnormal. By 8 years of age, most subjects have lost the ability to rise from the floor and to climb stairs, show an increasingly labored gait, and often fall while walking, which leads to use of mobility devices such as strollers and scooters. Subjects with DMD walk slower than healthy boys and spend less time walking⁵ and they are significantly less active compared to healthy boys of similar age^{5, 6}. By 10 to 14 years of age, most are wheelchair dependent. Weakness of the arms and increasingly limited upper limb function, contractures, decubitus ulcers, and scoliosis (which often requires surgery), occur frequently. While pulmonary and cardiac functions are generally normal during early childhood, cardiac and diaphragmatic muscles progressively weaken during late childhood and adolescence leading to eventual dependence on ventilation support. Historically, subjects typically died from respiratory or cardiac failure in their late teens or early 20s^{7, 8}. Recent research suggests that use of ventilation support and steroids may increase life span by several years; however, DMD still has a mortality rate of 100%⁹. Corticosteroids used for palliative treatment of DMD can prolong ambulation and reduce the incidence of severe scoliosis; however, they are often associated with serious side effects^{10, 11} and are not always employed.

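### Section 8.3 requires corticosteroids of boys over 5 but the eligibility criteria require them of nobody; the rules need reconciling, and post-Baseline steroid changes need flagging in the functional summaries

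*Combined protocol and SAP*

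**What the plan says.** Section 8.3 (Prior and Concomitant Medications) states that oral corticosteroids for DMD "are required for boys older than 5 years during the course of this study". It mentions neither ambulation nor any exemption for boys not yet treated. It then adds that "Subjects entering the study on corticosteroids must have been on a stable dose (or dose equivalent) of oral corticosteroids for at least 12 weeks" before the first dose, and that "Doses of corticosteroids are expected to remain constant" apart from weight adjustments, so far as is clinically feasible.

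Inclusion criterion 5 in Section 7.2, repeated in the Synopsis, is a conditional sentence. It opens "If the subject is ambulant and 4 years old or greater and has been on a stable dose or dose equivalent of oral corticosteroids", with a 12-week minimum before Week 1, and concludes that "the dose is expected to remain constant (except for modifications to accommodate changes in weight) throughout the study". The only age limit for entry is criterion 2: "Is above age 6 months".

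In Section 7.3 the nearest exclusion, number 7, reads: "Use of any pharmacologic treatment (other than corticosteroids) within 12 weeks prior to Week 1 that may have an effect on muscle strength or function". It exempts corticosteroids, so neither use nor non-use excludes a boy.

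On relevance to outcome, Section 4.1 says "Corticosteroids used for palliative treatment of DMD can prolong ambulation", and also notes that steroids are not used in every case.

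**The concern.** Two parts of the protocol govern steroid use and they do not describe the same boys. The eligibility list decides who enters, and Section 8.3 decides what must hold during the study. A boy over 5 who is not on steroids satisfies the first and fails the second. The site then has no written instruction on whether to screen him out, to enter him as a deviation, or to regard him as needing to start.

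If he starts after Baseline, the statistical difficulty lies in the functional data. There is no concurrent control, and Section 5.3 sets function against expected natural history. A treatment that the protocol itself says can prolong ambulation would then begin in the same interval as the study drug. His change from Baseline in NSAA, 100M or a timed test would contain both effects, with nothing in the design to separate them. The plan has no rule for presenting such a subject.

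**Working it through.** The main check is a comparison of text. The arithmetic only sizes the timing and tests the possible link to the primary analysis.

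**1. The rules side by side**

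| Feature | Inclusion 5 (7.2, Synopsis) | Section 8.3 |
|---|---|---|
| Age | 4 or greater | older than 5 |
| Ambulation | ambulant only | not mentioned |
| Already on steroids | a condition of the rule applying | not a condition |
| Obligation | keep an existing dose constant | be on steroids |

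They differ in every row.

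**2. A steroid-free boy over 5.** For inclusion 5 the condition is false, so it imposes nothing. No exclusion in Section 7.3 applies to him on this ground. He is eligible. Under Section 8.3 he must be on steroids during the study. Both hold only if he starts.

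**3. Can he start early enough to be stable by Week 1?** Screening and Baseline take about 8 weeks, and the stability period is 12 weeks. 12 − 8 = 4, so a boy who begins when screening opens is about 4 weeks short at Week 1. Unless entry is delayed, he either enters on a dose that has not been stable long enough or starts once treatment is under way.

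**4. A boy who passes the age on study.** 48 weeks / 52.18 weeks per year = 0.92 year, and 5.0 − 0.92 = 4.08 years. An untreated boy entering between about 4.1 and 5.0 years would pass the age before Week 48. This assumes that the rule follows current age rather than age at entry, and that it bites at the fifth birthday. The text settles neither point. Boys already on stable steroids are unaffected.

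**5. Which endpoints can be affected?**
- *Functional measures:* Section 4.1 gives a steroid effect on ambulation, and exclusion 7 treats steroids as the exception among agents that may alter strength or function. Section 4.3 reports that the external control in an earlier eteplirsen study was selected partly on steroid use. Confounding is therefore supported for NSAA, 100M and the timed tests. All are exploratory (Section 6.3.2.3), and Section 14.3.1.3 provides only for optional listings and descriptive summaries.
- *Dystrophin and splicing:* the documents give no steroid effect on western blot, immunofluorescence or RNA-Seq results.

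**6. Does it reach the primary test?** Section 14.3.1.1 states smallest two-sided p values of 0.0625 for 5 subjects and 0.03125 for 6. With all changes in one direction the formula is 2/2^n: 2/2^5 = 0.0625 and 2/2^6 = 0.03125. Both reproduce. The primary population is every dosed boy with western blot results at Baseline and Week 48. A steroid start does not remove a boy from it, so n stays where it was.

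**The case against.** The best defence is that Section 8.3 was meant as an entry rule: boys over 5 must already be on stable steroids. The section title covers prior medication, and the next sentence requires 12 weeks' stability. Its reference to subjects entering on corticosteroids can be explained by boys of 5 and under, who may enter without them. No passage tells anyone to start steroids. Enrolment is by invitation at one center, and eligibility is confirmed again at Baseline and Week 1, so a conflict may surface before dosing. This reading is possible, and a reader should not infer that the protocol definitely forces steroid starts. It does not remove the point: the condition would then be missing from Section 7.2 and the Synopsis, and the boy who passes the age on study would remain unaddressed.

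It can also be said that the data will be visible anyway. Section 14.4.3 records medication and dosage changes at each visit, Section 14.3.2.6 lists them, Section 14.4.5 lists deviations, and Section 14 foresees analysis for each subject. With about six boys, a reader could find a steroid start in the listings. That limits the damage, but the functional summaries would still pool that boy without comment.

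The constancy expectation in Section 8.3 is qualified by clinical feasibility, so it is not an absolute clash with the requirement.

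A reader might further infer that the primary test is at risk, because losing one of six boys moves the smallest attainable p from 0.03125 to 0.0625. The documents do not support this. The primary population keeps him. The withdrawal ground of erroneous inclusion in Section 7.5 covers boys who failed the eligibility criteria, and this boy met them. Other grounds are discretionary. The floor of six subjects applies to a loss for any reason and does not measure this defect.

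**Conclusion.** The inconsistency between Section 8.3 and inclusion 5 stands, on age, ambulation and obligation. A steroid-free boy over 5 is eligible as written but cannot satisfy Section 8.3 without starting treatment, and the text is unsettled for an untreated boy who passes the age on study.

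The statistical consequence is limited to the exploratory, descriptive functional measures, where a start after Baseline could not be told apart from drug effect. The documents give no size for the steroid effect. The number of boys concerned is unknown and lies between 0 and 6; one boy would be 1/6, or 17%, of the planned sample, which is an illustration and not an estimate. The conclusion assumes that at least one boy enters off steroids and starts after Baseline.

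It would go too far to say that change from Baseline is confounded in general. Bias in the western blot endpoint is not shown, nor is a reduction of the primary sample. This should be corrected because the protocol cannot be applied as written to a foreseeable boy, and because the correction is cheap.

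**What to change.** Reconcile Section 7.2 and the Synopsis with Section 8.3 on four matters: the age, whether ambulation matters, whether steroid use is a condition of entry, and what applies to a boy who passes the age during the 48 weeks. Which clinical rule is right is for the sponsor to decide.

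In Section 14.3.1.3, add that any subject whose steroid status changed after Baseline will be flagged in the functional listings and summaries, and that NSAA, 100M and timed-test results will be shown with and without him. The medication data are already collected at each visit, so no new assessment is needed.

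The cost is protocol wording, one flag and one additional descriptive summary. With so few boys the second summary will be sparse, and it should be read as a description only.
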